4.7 PATIENT, STUDY, AND SITE DISCONTINUATION

4.7.1 PATIENT DISCONTINUATION

The investigator has the right to discontinue a patient from STP1 or withdraw a patient from the study at any time. In addition, patients have the right to voluntarily withdraw from the study at any time for any reason. Reasons for discontinuation of STP1 or withdrawal from the study may include, but are not limited to, the following:

- Patient withdrawal of consent at any time.
- Any medical condition that the investigator or sponsor determines may jeopardize the patient's safety if he or she continues in the study.
- Investigator or sponsor determines it is in the best interest of the patient.
- Patient non-compliance.

Patients who fulfill the criteria described in the Stopping Rules section (as defined in [Section 3.1.2](#)) should be discontinued from the study.

4.7.1.1 DISCONTINUATION FROM STP1

Patient must discontinue STP1 if they experience any of the following:

- Pregnancy.
- Patient unable to continue to comply with study requirements.
- Unblinding of a patient.

Patients who discontinue STP1 prematurely will be asked to return to the clinic for a follow-up visit (see [Section 4.6.2.4](#)). The primary reason for premature STP1 discontinuation should be documented on the appropriate eCRF page. Patients who discontinue STP1 prematurely may be replaced to achieve a total of 16 patients.

4.7.1.2 WITHDRAWAL FROM STUDY

Every effort should be made to obtain information on patients who withdraw from the study. The sponsor or a designee should follow up by telephone or electronic mail. The primary reason for withdrawal from the study should be documented on the appropriate eCRF. The Study Monitor should include reviewing of subject withdrawals as part of the monitoring visit scope and Monitoring Plan.

Patients will not be followed for any reason after consent has been withdrawn.

Patients who withdraw consent may be replaced to achieve a total of 16 patients.

4.7.2 STUDY AND SITE DISCONTINUATION

The sponsor has the right to terminate this study at any time. Reasons for terminating the study may include, but are not limited to, the following:

- The incidence or severity of AE in this or other studies indicates a potential health hazard to patients.
- Patient enrollment is unsatisfactory.
- Important new information becomes available that may be relevant to the subject's consent.

The sponsor will notify the investigator and Health Authorities if the study is placed on hold, or if the sponsor decides to discontinue the study or development program.

The sponsor has the right to replace a site at any time. Reasons for replacing a site may include, but are not limited to, the following:

- Excessively slow recruitment.
- Poor protocol adherence.
- Inaccurate or incomplete data recording.
- Non-compliance with the International Council for Harmonisation (ICH) guideline for Good Clinical Practice (GCP).

5. ASSESSMENT OF SAFETY

5.1 SAFETY PARAMETERS AND DEFINITIONS

Safety assessments will consist of monitoring and recording the incidence, nature and severity of AEs, including SAEs and AEIs; measurement of protocol-specified safety laboratory assessments; and measurement of protocol-specified vital signs, ECGs and other protocol-specified tests described in [Section 5.1.4](#).

Certain types of events require immediate reporting to the sponsor, as outlined in [Section 5.4](#).

5.1.1 ADVERSE EVENTS

According to the ICH guideline for GCP, an AE is any untoward medical occurrence in a clinical investigation subject administered a pharmaceutical product, regardless of causal attribution. An AE can therefore be any of the following:

- Any unfavorable and unintended sign (including an abnormal laboratory finding), symptom, or disease temporally associated with the use of a medicinal product, whether or not considered related to the medicinal product.
- Any new disease or exacerbation of an existing disease (a worsening in the character, frequency, or severity of a known condition).
- Recurrence of an intermittent medical condition (e.g., headache) not present at baseline.
- Any deterioration in a laboratory value or other clinical test (e.g., ECG) that is associated with symptoms or leads to a change in study treatment or concomitant treatment or discontinuation from study drug(s).
- AEs that are related to a protocol-mandated intervention, including those that occur prior to assignment of study treatment (e.g., screening invasive procedures such as biopsies).

5.1.2 SERIOUS ADVERSE EVENTS (IMMEDIATELY REPORTABLE TO THE SPONSOR)

An SAE is any AE that meets any of the following criteria:

- Fatal (i.e., the AE actually causes or leads to death).
- Life-threatening (i.e., the AE, in the view of the investigator, places the patient at immediate risk of death). This does not include any AE that, had it occurred in a more severe form or was allowed to continue, might have caused death.
- Requires or prolongs in-patient hospitalization (see [Section 5.3.5.10](#)).
- Results in persistent or significant disability/incapacity (i.e., the AE results in substantial disruption of the patient's ability to conduct normal life functions).
- Congenital anomaly/birth defect in a neonate/infant born to a mother exposed to study drug(s).
- Significant medical event in the investigator's judgment (e.g., may jeopardize the patient's safety or may require medical/surgical intervention to prevent one of the outcomes listed above).

The terms "severe" and "serious" are not synonymous. Severity refers to the intensity of an AE (rated as mild, moderate or severe, or according to a pre-defined grading criterion; see [Section 5.3.3](#)); the event itself may be of relatively minor medical significance (such as severe headache without any further findings).

Severity and seriousness need to be independently assessed for each AE recorded on the eCRF.

SAEs are required to be reported by the investigator to the sponsor immediately (i.e., no more than 24 hours after learning of the event; see [Section 5.4.2](#) for reporting instructions).

5.1.3 ADVERSE EVENTS OF SPECIAL INTEREST (IMMEDIATELY REPORTABLE TO THE SPONSOR)

AESIs are required to be reported by the investigator to the sponsor immediately (i.e., no more than 24 hours after learning of the event; see [Section 5.4.2](#) for reporting instructions). AESIs for this study include the following:

- Electrolyte imbalance: hypokalemia (K⁺ level <3.4 mEq/L), hyperkalemia (>5.0 mEq/L), hyponatremia (Na⁺ level <135 mEq/L), hypochloremia (Cl⁻ level <97 mEq/L)
- Thrombocytopenia is defined as meeting one or both criteria:
 - Platelet count below $150 \times 10^9/L$ (or 150.000 platelets per microliter (mcL))
 - Platelet count drop of $\geq 50\%$ compared to baseline
- Drug-induced liver injury (DILI)
- Dehydration and orthostasis (defined by a fall in systolic blood pressure over 20 mm Hg or a fall in diastolic pressure over 10 mm Hg within 3 minutes of standing).

5.1.4 OTHER SAFETY ASSESSMENTS

Additional safety data will be obtained on the following:

- Changes from baseline in SBP, DBP, HR and respiratory rate.
- Changes from baseline in orthostatic measurements of BP and HR
- Changes from baseline in ECG parameters (HR, PQ, QRS, QT, RR and QTcF, along with information on T and U waves)
- Incidence of clinically significant ECG abnormalities
- Hearing assessment
- Incidence of laboratory abnormalities, based on hematology, blood chemistry, coagulation and urinalysis test results, as described in [Section 4.6.1.5](#).

5.2 SAFETY PLAN

The Safety Plan considers observations made in non-clinical investigations including GLP toxicology studies in rats and dogs and the observations made in clinical trials. Hypothetical considerations are included in the interpretation of non-clinical and clinical data.

The safety monitoring and the frequency of the scheduled visits are described in [Appendix 1](#). All safety data will be reviewed throughout the study by the sponsor in a treatment-blinded manner. However, the DSMB will review the blinded safety and tolerability data obtained from the first dose cohort (8 patients) who finish the 2 weeks of treatment and the 2 weeks of follow-up. The following sections specify some of the monitoring measures that will be taken to maximize the patient's safety in this study.

5.2.1 MANAGEMENT OF SPECIFIC ADVERSE EVENTS

5.2.1.1 ABNORMAL LABORATORY FINDINGS

Laboratory abnormalities reported with [REDACTED] included hyperuricemia (18.4%) and electrolytes imbalance (e.g., hypochloremia for 14.9% or hypokalemia for 14.7%). Hypokalemia was also observed in a [REDACTED] dose-dependent manner in the BUMEA trial [NCT01078714; Lemonnier et al, 2017]. In the current study, laboratory assessment will be done every week during the treatment period and at the end of the follow-up period. If hypokalemia is observed, potassium supplements should be administered, and patients should be advised to eat potassium-rich foods.

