Endpoints	
Primary Endpoints - Safety:
 
The safety outcome measures for this study are as follows:
 
• Incidence, nature and severity of adverse events (AEs).• Incidence, nature and severity of serious adverse events (SAEs).• Incidence, nature and severity of adverse events of special interest (AESIs).• Incidence, nature and severity of AEs leading to treatment discontinuation.• Changes from baseline in SBP, DBP, heart rate (HR) and respiratory rate.• Changes from baseline in orthostatic measurements of blood pressure (BP) and HR.• Changes from baseline in ECG parameters (HR, PQ, QRS, QT, RR and QTcF, along with information on T and U waves).• Incidence of clinically significant ECG abnormalities.• Hearing assessment.• Incidence of clinically relevant laboratory abnormalities, based on hematology, coagulation, blood chemistry and urinalysis test results:
○ Hematology: hemoglobin concentration, hematocrit level, erythrocytes and platelet counts, leucocytes differential (absolute) counts (neutrophils, eosinophils, lymphocytes, monocytes and basophils)○ Coagulation: international normalized ratio (INR), activated partial thromboplastin time (aPTT) and prothrombin time (PT)○ Blood chemistry: C-reactive protein (CRP test), aspartate aminotransferase (AST), alanine aminotransferase (ALT), gamma-glutamyl-transferase (GGT), total and conjugated bilirubin, alkaline phosphatase (ALP), albumin, creatine phosphokinase (CPK), creatinine, urea, total protein, total cholesterol, triglycerides, glucose, sodium, chloride, calcium, magnesium, phosphate, potassium○ Urinalysis: protein, blood, glucose, leucocytes, nitrites, pH and crystals.• Incidence of value outside of the normal ranges and of clinically relevant blood chemistry test results for electrolytes:
○ Sodium, chloride, calcium, magnesium, phosphate, potassium 
Secondary Endpoints - Pharmacokinetics:
 
• [REDACTED] plasma concentration will be evaluated at Days 1, 7, and 14 to 18.• Plasma concentrations of [REDACTED] and associated PK parameters: Area under the plasma concentration-time curve ($AUC_{0-\tau}$, $AUC_{0-\text{last}}$, $AUC_{0-\infty}$), minimum plasma concentration prior to administration (C_{trough}), maximum plasma concentration (C_{max}, $C_{\text{max,ss}}$), time of
-----------	--

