1.5.2 BENEFIT-RISK ASSESSMENT

[REDACTED] is a brain penetrant PDE3, PDE4, PDE10 and PDE11 inhibitor. [REDACTED] has been marketed [REDACTED]. Recommended dosing is [REDACTED].

[REDACTED] Recommended dosing is [REDACTED] mg orally twice a day for asthma. In published studies of [REDACTED] with doses up to 100 mg/day, the most common AEs were headaches and GI effects (e.g., nausea,

diarrhea, and elevated liver enzymes). Rare cases of thrombocytopenia have also been reported. [REDACTED] has anti-inflammatory effects and is predicted to have therapeutic effects for patients with ASD-Phen1 because these patients are thought to have an inflammatory-specific phenotype. Beneficial activity has been reported in rodent models of inflammatory-based brain disorders.

[REDACTED] marketed in the United States [REDACTED] is a potent NKCC1 inhibitor that acts as a loop diuretic. It has been administered in doses of 0.5, 1, or 2 mg twice a day for up to three months in a randomized, double-blind, placebo-controlled trial of 88 children and adolescents (ages 2 to 18 years) with ASD [Lemonnier et al, 2017]. Statistically significant improvements on an autism rating scale (Childhood Autism Rating Scale [CARS]) and an autism severity scale (Social Responsiveness Scale, 2nd Edition [SRS-2]) were reported with [REDACTED] therapy over placebo among study completers. AEs were dose-related, the most common being hypokalemia, increased diuresis, loss of appetite, dehydration and asthenia. Six of 21 patients in the 2 mg twice a day group dropped out because of an AE, most frequently hypokalemia. Hypokalemia occurred generally at the beginning of treatment and improved gradually with oral potassium supplementation and potassium-rich foods. The [REDACTED] twice a day dose appeared to provide the best balance between safety and efficacy. To minimize the risk of hypokalemia, concomitant use of other loop diuretics (e.g., furosemide) will not be permitted during the study and electrolyte levels will be closely monitored. In the event of confirmed hypokalemia, potassium supplementation will be prescribed.

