3.3 OUTCOME MEASURES

3.3.1 SAFETY OUTCOME MEASURES

The safety outcome measures for this study are as follows:

- Incidence, nature and severity of AEs.
- Incidence, nature and severity of SAEs.
- Incidence, nature and severity of AESIs.
- Incidence, nature and severity of AEs leading to treatment discontinuations.
- Changes from baseline in systolic blood pressure (SBP), diastolic blood pressure (DBP), heart rate (HR) and respiratory rate.
- Changes from baseline in orthostatic measurements of BP and HR.
- Changes from baseline in ECG parameters (HR, PQ, QRS, QT, RR and QTcF, along with information on T and U waves).
- Incidence of clinically significant ECG abnormalities.
- Hearing assessment
- Incidence of clinically relevant laboratory abnormalities, based on hematology, blood chemistry and urinalysis test results:
 - Hematology: hemoglobin, hematocrit, erythrocytes, platelet count, leucocytes differential (absolute) counts (neutrophils, eosinophils, lymphocytes, monocytes, basophils).
 - Blood chemistry: aspartate aminotransferase (AST), alanine aminotransferase (ALT), gamma-glutamyltransferase (GGT), total and conjugated bilirubin, alkaline phosphatase (ALP), albumin, creatine phosphokinase (CPK), creatinine, urea, total protein, total cholesterol, triglycerides, sodium, chloride, calcium, magnesium, phosphate, potassium, glucose.
- Incidence of value outside of the normal ranges of blood chemistry test results for electrolytes:
 - Sodium, chloride, calcium, magnesium, phosphate, potassium
- Urinalysis: protein, blood, glucose, leucocytes, nitrites, pH, and presence of crystals.

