4.6.1.5 LABORATORY ASSESSMENTS

Normal ranges for the study laboratory parameters must be supplied to the sponsor before the study starts. Laboratory safety tests shall be collected at time-points specified in the Schedule of Assessments ([Appendix 1](#)).

Additional blood or urine samples may be taken at the discretion of the investigator if the results of any test fall outside the reference ranges, or clinical symptoms necessitate additional testing to monitor patient's safety. Where the clinical significance of abnormal laboratory results is considered uncertain, screening laboratory tests may be repeated before randomization to confirm eligibility. If there is an alternative explanation for a positive urine or blood test for drugs of abuse, e.g., previous occasional intake of a medication or food-containing for example, codeine, benzodiazepines or opiates, the test could be repeated to confirm washout.

In the event of unexplained abnormal clinically significant laboratory test values, the tests should be repeated immediately and followed up until they have returned to the normal range and/or an adequate explanation of the abnormality is found. Results of clinical laboratory testing will be recorded on the eCRF or be received as electronically produced laboratory reports submitted directly from the local or central laboratory.

When a fasted state is required, subjects have to be fasted for at least 4 hours.

Blood samples for the following laboratory tests will be sent to the local laboratory(ies) for analysis.

- Hematology (5 mL per sample): hemoglobin, hematocrit, erythrocytes, platelet count, leucocytes differential (absolute) counts (neutrophils, eosinophils, lymphocytes, monocytes, basophils).

- Blood chemistry (5 mL per sample): C-reactive protein (CRP test), AST, ALT, GGT, total and conjugated bilirubin, alkaline phosphatase (ALP), lactate, pyruvate, albumin, creatine phosphokinase (CPK), creatinine, urea, total protein, total cholesterol, triglycerides, sodium, chloride, calcium, magnesium, phosphate, potassium, glucose.
- Coagulation (2 mL per sample): international normalized ratio (INR), activated partial thromboplastin time (aPTT), prothrombin test (PT).
- Viral serology (2 mL per sample):
 - HIV (specific tests HIV-1 antibody).
 - Hepatitis B surface antigen (HBsAg).
 - Total hepatitis B core antibody (HBcAb).
 - Hepatitis C virus (HCV) antibody.

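### Hyperuricemia has the highest rate among the laboratory abnormalities the protocol lists for the diuretic component, yet uric acid is in no scheduled chemistry panel, so the trial will give no incidence or change from baseline for it by treatment group

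*Protocol*

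**What the plan says.** Protocol Section 5.2.1.1 describes laboratory abnormalities reported with one component. They "included hyperuricemia (18.4%) and electrolytes imbalance (e.g., hypochloremia for 14.9% or hypokalemia for 14.7" per cent. It then says that laboratory tests will be done weekly during treatment and again at the end of follow-up.

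The component's name is blacked out. The next sentence refers to dose-dependent hypokalemia in a pediatric trial that Section 1.5.2 cites for the component that "is a potent NKCC1 inhibitor that acts as a loop diuretic", so the diuretic is meant.

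The primary laboratory endpoint in the Synopsis is "Incidence of clinically relevant laboratory abnormalities, based on hematology, coagulation, blood chemistry and urinalysis test results". Section 3.3.1 has nearly the same: "Incidence of clinically relevant laboratory abnormalities, based on hematology, blood chemistry and urinalysis test results". Section 5.1.4 ties the laboratory abnormalities to the tests described in Section 4.6.1.5.

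The chemistry panel is listed three times. From albumin onward, Section 4.6.1.5 reads "albumin, creatine phosphokinase (CPK), creatinine, urea, total protein, total cholesterol, triglycerides, sodium, chloride, calcium, magnesium, phosphate, potassium, glucose". The Synopsis has "creatine phosphokinase (CPK), creatinine, urea, total protein, total cholesterol, triglycerides, glucose, sodium, chloride, calcium, magnesium, phosphate, potassium". Section 3.3.1 gives the same set of analytes in the order of Section 4.6.1.5. Urea and creatinine are there each time; uric acid never is. Urinalysis covers crystals but not uric acid.

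SAP Section 4.2 analyses laboratory data by test category and names no further analyte.

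**The concern.** Safety and tolerability are the primary objective. Section 1.5.1 says the diuretic dose is kept the same in both cohorts so as to gather enough safety and tolerability data to support Phase 2. Describing the laboratory effects of the diuretic when given in the combination is therefore part of the purpose.

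Section 5.2.1.1 names three abnormalities and relies on scheduled laboratory tests, but those tests cover only the two with the lower rates. No reason for the omission is given. Followed as written, SAP Table 20 (summary statistics), Table 25 (shift by clinical significance), listing DL7 and the laboratory data sent to the DSMB will contain no uric acid result, whatever happens in the patients. A Phase 2 planner would have no figure by treatment group, and could overlook that none was collected.

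**Working it through.** **The plan's own figure.** The only calculated design figure is the number randomized: 16 completers with about 20% dropout gives 16/(1 − 0.20) = 20, as stated. The point does not depend on it. The plan states no detection probability.

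**Is the analyte really absent?**
- Rates listed in Section 5.2.1.1: 18.4% (hyperuricemia) > 14.9% (hypochloremia) > 14.7% (hypokalemia).
- Chloride and potassium are in all three chemistry lists. Uric acid is in none.
- The SAP electrolyte tables cover sodium, chloride, calcium, magnesium, phosphate and potassium only.
- Hyperuricemia is not an adverse event of special interest (Section 5.1.3).

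**How many active patients could still be measured?**
- Planned active places: up to 6 per dose level, so up to 12 (Section 6.1). The minimum at the highest dose is 3 (Synopsis).
- SAP Section 5.1 says the first 4 patients followed the sampling schedule in force before protocol Version 4.0. The current protocol is Version 6.
- Cohort 1 has 2 placebo places, so at least 4 − 2 = 2 of those 4 were on active, unless replaced. The ceiling for a change made now is 12 − 2 = 10. The true number is probably lower; the documents do not give enrolment status.

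**What would measurement show?** Assumption: each active patient has probability p of hyperuricemia, independently. Then P(at least one case) = 1 − (1 − p)^n, and the expected number of cases is n × p. The second rate is half of the first (18.4/2 = 9.2%). It is my assumption, added because it is unknown whether 18.4% transfers to this trial.

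| Active patients measured (n) | Expected cases, p = 18.4% | P(≥1), p = 18.4% | P(≥1), p = 9.2% |
|---|---|---|---|
| 3 | 0.55 | 1 − 0.816^3 = 45.7% | 1 − 0.908^3 = 25.1% |
| 6 | 1.10 | 1 − 0.816^6 = 70.5% | 1 − 0.908^6 = 44.0% |
| 10 (ceiling) | 1.84 | 1 − 0.816^10 = 86.9% | 1 − 0.908^10 = 61.9% |

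For comparison, hypokalemia at its listed 14.7%, which is measured, gives 37.9% with n = 3 and 61.5% with n = 6. The unmeasured abnormality would be at least as visible as one that the plan does track.

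**The case against.** The strongest reply is that this is an unexplained omission and not a contradiction. No section promises to measure uric acid, and Section 5.2.1.1 names a response only for hypokalemia. That is true, but the section still sets scheduled laboratory tests against abnormalities that they cover only in part.

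Four stronger readings are tempting, and the documents do not support them.

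- *The trial cannot detect hyperuricemia at all.* Section 4.6.1.5 allows additional samples at the investigator's discretion, and Section 5.3.5.4 records symptomatic or clinically significant laboratory findings as adverse events. A case could surface that way. Neither route yields a systematic incidence by group.
- *Hyperuricemia is the abnormality the protocol expects most often, with about 2.2 cases (12 × 0.184) and a 91% chance of at least one in 12 active patients.* The 18.4% comes with no dose, duration, population or threshold. The electrolyte figures are given as examples, so the combined electrolyte rate may be higher. Sections 1.4.2 and 1.5.2 do not name hyperuricemia among the most frequent events in the pediatric ASD trials. The endpoint counts clinically relevant abnormalities, and not every case would qualify. Twelve active patients is also out of reach, as shown above.
- *Measurement would show whether the partner drug changes the diuretic's effect.* Each cohort compares the combination with placebo. No arm receives the diuretic alone, so that effect could not be isolated.
- *The tables would report a normal result.* Table 20 is organised by named parameter and would simply have no uric acid row. The risk is that a reader takes the missing row for a negative finding, which one sentence in the report would prevent.

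**Conclusion.** The point stands as a gap in the primary safety description that is cheap to close. It does not threaten the validity of the trial. Of the three abnormalities that Section 5.2.1.1 lists for the diuretic component, the one with the highest rate has no scheduled measurement, and the SAP does not supply one.

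If the 18.4% carried over, prospective measurement would show at least one case among active patients with a chance of about 46% (n = 3), 71% (n = 6) and at most about 87% (n = 10). At half that rate the figures are 25%, 44% and 62%. They are illustrative and describe any hyperuricemia, not only clinically relevant cases. The omission itself does not depend on them. Raw values and change from baseline would be informative even if no case were judged clinically relevant, because SAP Section 4.2 summarises both for every quantitative parameter.

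Two assumptions remain: that the blacked-out name in Section 5.2.1.1 is the diuretic, which the surrounding text supports, and that enrolment was still open when a change could take effect.

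**What to change.** - Add serum uric acid to the chemistry lists in the Synopsis and Sections 3.3.1 and 4.6.1.5, at the chemistry visits already in Appendix 1 (Screening, Days 7, 14 and 28), for remaining patients. Use the existing chemistry sample if the local laboratory confirms that the volume suffices.
- Add it to SAP Tables 20 and 25 and listing DL7. The SAP takes Screening as the laboratory baseline, so only patients screened after the change will have a change from baseline.
- State in the report that earlier patients have no uric acid values, and give the number measured in each group, so that absence from the tables is not read as a negative finding.
- If the sponsor decides not to measure it, say why in Section 5.2.1.1 and report the gap as a limitation.

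The cost is one analyte at existing visits, a small protocol and SAP amendment with IRB approval (Section 9.5), and a consent revision if required (Section 8.2). No extra visit is needed. The data will be incomplete, because patients already treated cannot be measured retrospectively unless serum was stored.
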